For Part I, nivolumab and ipilimumab are administered every 3 weeks for 4 doses (Table 5.1-2). If subjects discontinue therapy during Part I, nivolumab monotherapy can be continued as

described in [Section 4.5.5](#). **For Part II**, nivolumab monotherapy is administered every 2 weeks ([Table 5.1-3](#)) until 24 months after the first combination dose (Part I and II). Subjects may be treated for more than 24 months for a maximum of 50 cycles in case an on-hold period occurs during the Treatment Phase.

Windows for dosing of both Part I and Part II are discussed in [Section 4.5](#).

An initial tumor assessment is to be completed at Week 12 (± 5 days) after the first treatment dose. Further tumor assessments are recommended to be completed as required by local standards of care or at the investigator's discretion and are recommended every 8 weeks until documented tumor progression.

Subjects treated with the study drugs will be permitted to continue treatment beyond initial PD as assessed by the investigator's clinical judgment and local standards of care as long as they meet the criteria specified in [Section 4.5.8](#).

The Treatment Phase ends when the subject is discontinued from study therapy. For a complete list of reasons for treatment discontinuation, see [Sections 3.5](#) and [4.5.6](#).

The Follow-up Phase begins when the decision to discontinue a subject from study therapy is made (no further treatment with study therapy) ([Table 5.1-4](#) and [Table 5.1-5](#)):

- Subjects who discontinue therapy in Part I are recommended to be followed by direct contact (office visit) every 4 weeks for up to 100 days after the last dose of combination regimen therapy. After completion of the onsite follow-up visits (for up to 100 days), subjects will be followed every 24 weeks ± 2 weeks for survival either by direct visit or via telephone contact. OS will be followed from the start of therapy up to 2 years or until death, withdrawal of study consent, or lost-to-follow-up, whichever comes first.

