If both nivolumab and ipilimumab are discontinued during Part I due to an AE, a subject may begin nivolumab monotherapy (Part II) providing the following conditions are met:

- The adverse event has resolved to Grade \leq 1 or baseline within 12 weeks.
- Subjects had no prior life-threatening AEs.
- In investigator's opinion, the subject may derive a clinical benefit from continuation of nivolumab monotherapy treatment.
- Restrictions in [Section 4.5.5](#), Criteria to Resume Treatment are met.
- Restrictions in [Section 3.4](#), any concurrent antineoplastic therapy (ie, chemotherapy, hormonal therapy, immunotherapy, non-palliative radiation therapy, or standard or investigational agents for treatment of cancer) are met.

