4.5.6 Discontinuation Criteria

Discontinuation criteria apply for all drug-related AEs attributed to nivolumab, ipilimumab, or both.

Nivolumab treatment should be permanently discontinued for the following:

- Any Grade 2 drug-related uveitis, eye pain, or blurred vision that does not respond to topical therapy and does not improve to Grade 1 severity within the re-treatment period OR requires systemic treatment
- Any Grade 3 non-skin, drug-related adverse event lasting $>$ 7 days, or recurs with the following exceptions for laboratory abnormalities, diarrhea, colitis, neurologic toxicity, drug-related uveitis, pneumonitis, bronchospasm, hypersensitivity reactions, infusion reactions, and endocrinopathies
 - Grade 3 drug-related diarrhea, colitis, neurologic toxicity, uveitis, pneumonitis, bronchospasm, myocarditis, hypersensitivity reaction, or infusion reaction of any duration requires discontinuation.
 - Grade 3 drug-related endocrinopathies adequately controlled with only physiologic hormone replacement do not require discontinuation. Adrenal insufficiency requires discontinuation regardless of control with hormone replacement.
 - Grade 3 drug-related laboratory abnormalities do not require treatment discontinuation except:
 - ◆ Grade 3 drug-related thrombocytopenia $>$ 7 days or associated with bleeding requires discontinuation
 - ◆ Any drug-related liver function test (LFT) abnormality that meets the following criteria require discontinuation:
 - Grade \geq 3 drug-related AST, ALT, or total bilirubin requires discontinuation

NOTE: In most cases of Grade 3 AST or ALT elevation, study drugs will be permanently discontinued. If the investigator determines a possible

favorable benefit/risk ratio that warrants continuation of study drug(s), a discussion between the investigator and the BMS Medical Monitor/designee must occur.

- Concurrent AST or ALT > 3 x ULN and total bilirubin > 2 x ULN
- Any Grade 4 drug-related AE or laboratory abnormality, except for the following events which do not require discontinuation:
 - Grade 4 neutropenia ≤ 7 days
 - Grade 4 lymphopenia or leukopenia or asymptomatic amylase or lipase
 - Isolated Grade 4 electrolyte imbalances/abnormalities that are not associated with clinical sequelae and are corrected with supplementation/appropriate management within 72 hours of their onset

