 - Grade 4 drug-related endocrinopathy adverse events, such as, hyper- or hypothyroidism, or glucose intolerance, which resolve or are adequately controlled with physiologic hormone replacement (corticosteroids, thyroid hormones) or glucose-controlling agents, respectively, may not require discontinuation after discussion with and approval from the BMS Medical Monitor.
- Any dosing interruption lasting > 12 weeks with the following exceptions:
 - Dosing interruptions to allow for prolonged steroid tapers to manage drug-related AEs are allowed.
 - Dosing interruptions > 12 weeks that occur for non-drug-related reasons may be allowed if approved by the BMS medical monitor.
 - Prior to re-initiating treatment in a subject with a dosing interruption lasting > 12 weeks, the BMS medical monitor must be consulted. Tumor assessments should continue as per protocol even if dosing is interrupted.
- Any adverse event, laboratory abnormality, or intercurrent illness which, in the judgment of the investigator, presents a substantial clinical risk to the subject with continued nivolumab or ipilimumab dosing.

As described in [Section 4.5.3](#), refer to the nivolumab Investigator's Brochure for management of AEs associated with I-O agents.

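### The Grade 4 endocrinopathy exception in Protocol 4.5.6 does not exclude adrenal insufficiency, which 4.5.5 says must stop treatment; 4.5.6 also lacks a link to Part II re-entry

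*Protocol*

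**What the plan says.** **Adrenal insufficiency.** The Protocol deals with it in three places.

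- Section 4.5.5 lets controlled endocrinopathies resume, but requires discontinuation for adrenal insufficiency of Grade 3 or higher whatever the hormone control.
- Section 4.5.6 repeats that requirement inside its Grade 3 endocrinopathy item. The sentence there carries no grade of its own.
- The Grade 4 part of Section 4.5.6 lists exceptions to stopping. One covers endocrinopathies, with thyroid disorders and glucose intolerance as examples, that resolve or are controlled with hormone replacement or glucose-controlling agents. Corticosteroids are named among the replacement hormones. Continuation needs discussion with the Medical Monitor and the Monitor's approval.

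**Part II re-entry.** The list in Section 4.5.6 opens with "Nivolumab treatment should be permanently discontinued for the following" and applies whichever drug is blamed. One item states: "Grade 3 drug-related diarrhea, colitis, neurologic toxicity, uveitis, pneumonitis, bronchospasm, myocarditis, hypersensitivity reaction, or infusion reaction of any duration requires discontinuation". Section 4.5.5 states: "If both nivolumab and ipilimumab are discontinued during Part I due to an AE, a subject may begin nivolumab monotherapy (Part II"), if conditions are met. These are recovery to Grade 1 or baseline within 12 weeks, investigator-judged benefit, the concurrent-therapy restrictions of Section 3.4, and "Subjects had no prior life-threatening AEs". A further condition refers back to the restrictions of Section 4.5.5 and ends "Criteria to Resume Treatment are met". Section 3.1 points the same way: "If subjects discontinue therapy during Part I, nivolumab monotherapy can be continued as" described in Section 4.5.5.

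**The concern.** Sections 4.5.5 and 4.5.6 give different answers for Grade 4 adrenal insufficiency. Section 4.5.6, taken alone, has an absolute stop under its Grade 3 item and a discretionary route at Grade 4. A site that consults only the discontinuation criteria could ask for approval to continue a subject whom Section 4.5.5 says must stop.

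The second matter is narrower. Section 4.5.6 calls the stop permanent and does not mention that Section 4.5.5 may lead to nivolumab again. What is at stake is re-exposure after a Grade 3 immune-related event, and whether a monitor can tell a permitted restart from a deviation.

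**Working it through.** The plan gives no figure on this point, so the check is a comparison of texts.

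**Step 1. Adrenal insufficiency by grade.**

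| Grade | Section 4.5.5 | Section 4.5.6 |
|---|---|---|
| 3 | Stop, whatever the hormone control | Stop, whatever the hormone control |
| 4 | Stop (the rule is Grade 3 or higher) | Stop, unless a controlled endocrinopathy is approved to continue; adrenal insufficiency is not excluded |

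The Grade 3 row agrees. The Grade 4 row does not.

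**Step 2. Does the exception reach adrenal insufficiency?** On its wording, yes. It applies to endocrinopathies generally, and its thyroid and glucose cases are only examples. It names corticosteroids as replacement, which is not the replacement hormone for either example. SAP Table A-2 places adrenal disorders within the endocrine category.

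**Step 3. Does another rule catch the case?** The re-entry condition on life-threatening events acts only after both drugs have been stopped in Part I. The Grade 4 exception operates by not stopping them. The catch-all in Section 4.5.6, for an event that "presents a substantial clinical risk to the subject with continued nivolumab or ipilimumab dosing", depends on investigator judgment. That leaves the Section 4.5.5 rule itself, and nothing visible says that it overrides the exception.

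**Step 4. Re-entry, worked on one case.** Take Grade 3 colitis in Part I, back to baseline within 12 weeks, with corticosteroids at or below 10 mg/day prednisone equivalent.

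- Section 4.5.6: nivolumab stops permanently.
- Section 4.5.5: Part II nivolumab may begin if the remaining conditions are met.

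**Step 5. Counts from the text.**

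- Grade 3 event types in the quoted Section 4.5.6 item: 9.
- Of these, named in Section 4.5.5 as a bar to resuming: 0 of 9.
- Given a return-to-baseline condition there: 3 of 9 (diarrhea, colitis, and pneumonitis as pulmonary toxicity).
- Section 4.5.6 events that Section 4.5.5 does name as bars: 2 (combined AST/ALT and bilirubin elevation; adrenal insufficiency of Grade 3 or higher). Re-entry inherits both, because it requires the Section 4.5.5 restrictions to be met.

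The zero does not by itself show a fault. A deliberate exception would look the same.

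**Step 6. Which reading does the text favour?** The exception. Re-entry presupposes that both drugs have been discontinued for an adverse event, Section 3.1 points to it, and it screens out life-threatening events. If every Section 4.5.6 stop also barred Part II, the catch-all would leave the re-entry rule almost nothing to do.

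**Step 7. Is that relation stated?** No. Section 4.5.5 cites Section 4.5.6 for delays over 12 weeks and for the combined liver criterion, but not for re-entry. Section 4.5.6 writes out other exceptions, for example "In most cases of Grade 3 AST or ALT elevation, study drugs will be permanently discontinued" followed by a benefit/risk discussion with the Medical Monitor. It does not write out this one.

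**The case against.** **On adrenal insufficiency.** Section 4.5.5 is mandatory and includes Grade 4. The Section 4.5.6 exception is permissive, its examples are not adrenal, and nothing happens without the Medical Monitor's approval. The adrenal sentence under the Grade 3 item has no grade and could be read more widely. All of this lowers the practical risk and is why the point is minor. It does not remove the conflict: that sentence sits under Grade 3 and is not repeated in the Grade 4 exception.

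**On re-entry.** The strongest reply is that a specific rule for Part I discontinuations stands beside a general one, so only a cross-reference is missing. That stands.

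A reader might infer more in three ways:

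- *That the two sections flatly contradict each other and send sites to opposite decisions.* The documents do not support this. Re-entry starts from discontinuation, and it rests on investigator judgment, so some variation between sites is intended. It is also guarded by the 12-week recovery limit, the steroid limit and the exclusion of prior life-threatening events.
- *That Grade 3 infusion reactions must bar Part II because Section 4.5.7 repeats the permanent stop.* Section 4.5.7 does not address Part II, and Section 4.5.6 lists infusion reactions on the same footing as the other eight events. Adding that bar, or a Medical Monitor step for re-entry after Grade 3 AST/ALT elevation, would be new clinical policy.
- *That the primary result is affected.* A subject already counted for a Part I event stays counted. The documents give no basis for sizing any other effect.

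**Conclusion.** The adrenal point holds: two stated safety rules conflict at Grade 4, and the wording of Section 4.5.6 should change. It is minor. It concerns one event type at one grade, behind a Medical Monitor approval step.

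The re-entry point holds only as a clarification. Section 4.5.5 is most likely a deliberate exception to the permanent stop, and Section 4.5.6 should say so. Whether all nine listed Grade 3 events should allow re-entry is a clinical question that the visible text does not settle.

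The number of subjects affected is not given and is not estimated. The conclusion assumes that no unseen text reconciles the rules: Section 3.4 and Appendix 1 are not visible. Section 4.5.5 describes the former as restricting concurrent antineoplastic therapy. Section 4.5.3 describes the latter as recommended management algorithms. Neither is an obvious place for such a rule, but this cannot be checked.

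**What to change.** 1. In the Grade 4 endocrinopathy exception of Section 4.5.6, insert *other than adrenal insufficiency* directly after the words that name Grade 4 drug-related endocrinopathy events. This brings the exception into line with Section 4.5.5.
2. In Section 4.5.6, add a cross-reference to the Part II re-entry conditions in Section 4.5.5.
3. Before wording item 2, have the sponsor's clinicians decide which of the listed Grade 3 events, if any, remain a bar to Part II nivolumab, and state the answer. Myocarditis, neurologic toxicity and infusion reaction are obvious candidates to discuss. A bare cross-reference would expressly open re-entry after all nine.

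The cost is two short wording changes and one clinical decision in a protocol amendment, with the usual ethics committee review. No new procedure or data collection is needed, and the sample size and planned analyses are unchanged.

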4.5.6 Discontinuation Criteria

Discontinuation criteria apply for all drug-related AEs attributed to nivolumab, ipilimumab, or both.

Nivolumab treatment should be permanently discontinued for the following:

- Any Grade 2 drug-related uveitis, eye pain, or blurred vision that does not respond to topical therapy and does not improve to Grade 1 severity within the re-treatment period OR requires systemic treatment
- Any Grade 3 non-skin, drug-related adverse event lasting $>$ 7 days, or recurs with the following exceptions for laboratory abnormalities, diarrhea, colitis, neurologic toxicity, drug-related uveitis, pneumonitis, bronchospasm, hypersensitivity reactions, infusion reactions, and endocrinopathies
 - Grade 3 drug-related diarrhea, colitis, neurologic toxicity, uveitis, pneumonitis, bronchospasm, myocarditis, hypersensitivity reaction, or infusion reaction of any duration requires discontinuation.
 - Grade 3 drug-related endocrinopathies adequately controlled with only physiologic hormone replacement do not require discontinuation. Adrenal insufficiency requires discontinuation regardless of control with hormone replacement.
 - Grade 3 drug-related laboratory abnormalities do not require treatment discontinuation except:
 - ◆ Grade 3 drug-related thrombocytopenia $>$ 7 days or associated with bleeding requires discontinuation
 - ◆ Any drug-related liver function test (LFT) abnormality that meets the following criteria require discontinuation:
 - Grade \geq 3 drug-related AST, ALT, or total bilirubin requires discontinuation

NOTE: In most cases of Grade 3 AST or ALT elevation, study drugs will be permanently discontinued. If the investigator determines a possible

favorable benefit/risk ratio that warrants continuation of study drug(s), a discussion between the investigator and the BMS Medical Monitor/designee must occur.

- Concurrent AST or ALT > 3 x ULN and total bilirubin > 2 x ULN
- Any Grade 4 drug-related AE or laboratory abnormality, except for the following events which do not require discontinuation:
 - Grade 4 neutropenia ≤ 7 days
 - Grade 4 lymphopenia or leukopenia or asymptomatic amylase or lipase
 - Isolated Grade 4 electrolyte imbalances/abnormalities that are not associated with clinical sequelae and are corrected with supplementation/appropriate management within 72 hours of their onset
 - Grade 4 drug-related endocrinopathy adverse events, such as, hyper- or hypothyroidism, or glucose intolerance, which resolve or are adequately controlled with physiologic hormone replacement (corticosteroids, thyroid hormones) or glucose-controlling agents, respectively, may not require discontinuation after discussion with and approval from the BMS Medical Monitor.
- Any dosing interruption lasting > 12 weeks with the following exceptions:
 - Dosing interruptions to allow for prolonged steroid tapers to manage drug-related AEs are allowed.
 - Dosing interruptions > 12 weeks that occur for non-drug-related reasons may be allowed if approved by the BMS medical monitor.
 - Prior to re-initiating treatment in a subject with a dosing interruption lasting > 12 weeks, the BMS medical monitor must be consulted. Tumor assessments should continue as per protocol even if dosing is interrupted.
- Any adverse event, laboratory abnormality, or intercurrent illness which, in the judgment of the investigator, presents a substantial clinical risk to the subject with continued nivolumab or ipilimumab dosing.

As described in [Section 4.5.3](#), refer to the nivolumab Investigator's Brochure for management of AEs associated with I-O agents.

4.5.7 Treatment of Nivolumab- or Ipilimumab-Related Infusion Reactions

Since nivolumab and ipilimumab contain only human immunoglobulin protein sequences, they are unlikely to be immunogenic and induce infusion or hypersensitivity reactions. However, if such a reaction were to occur, it might manifest with fever, chills, rigors, headache, rash, pruritis, arthralgias, hypo- or hypertension, bronchospasm, or other symptoms. All Grade 3 or 4 infusion reactions should be reported within 24 hours to the BMS Medical Monitor and reported as an SAE if criteria are met. Infusion reactions should be graded according to NCI CTCAE (version 4.0) guidelines.

Treatment recommendations are provided below and may be modified based on local treatment standards and guidelines as appropriate:

For Grade 1 symptoms: (Mild reaction; infusion interruption not indicated; intervention not indicated)

Remain at bedside and monitor subject until recovery from symptoms. The following prophylactic premedications are recommended for future infusions: diphenhydramine 50 mg (or equivalent) and/or paracetamol 325 to 1000 mg (acetaminophen) at least 30 minutes before additional nivolumab administrations.

For Grade 2 symptoms: (Moderate reaction requires therapy or infusion interruption but responds promptly to symptomatic treatment [eg, antihistamines, non-steroidal anti-inflammatory drugs, narcotics, corticosteroids, bronchodilators, IV fluids]; prophylactic medications indicated for ≤ 24 hours).

Stop the nivolumab or ipilimumab infusion, begin an IV infusion of normal saline, and treat the subject with diphenhydramine 50 mg IV (or equivalent) and/or paracetamol 325 to 1000 mg (acetaminophen); remain at bedside and monitor subject until resolution of symptoms. Corticosteroid or bronchodilator therapy may also be administered as appropriate. If the infusion is interrupted, then restart the infusion at 50% of the original infusion rate when symptoms resolve; if no further complications ensue after 30 minutes, the rate may be increased to 100% of the original infusion rate. Monitor subject closely. If symptoms recur then no further nivolumab or ipilimumab will be administered at that visit. Administer diphenhydramine 50 mg IV, and remain at bedside and monitor the subject until resolution of symptoms. The amount of study drug infused must be recorded on the electronic case report form (eCRF). The following prophylactic premedications are recommended for future infusions: diphenhydramine 50 mg (or equivalent) and/or paracetamol 325 to 1000 mg (acetaminophen) should be administered at least 30 minutes before additional nivolumab or ipilimumab administrations. If necessary, corticosteroids (recommended dose: up to 25 mg of IV hydrocortisone or equivalent) may be used.

For Grade 3 or Grade 4 symptoms: (Severe reaction, Grade 3: prolonged [ie, not rapidly responsive to symptomatic medication and/or brief interruption of infusion]; recurrence of symptoms following initial improvement; hospitalization indicated for other clinical sequelae [eg, renal impairment, pulmonary infiltrates]). Grade 4: (life-threatening; pressor or ventilatory support indicated).

Immediately discontinue infusion of nivolumab or ipilimumab. Begin an IV infusion of normal saline, and treat the subject as follows. Recommend bronchodilators, epinephrine 0.2 to 1 mg of a 1:1,000 solution for subcutaneous administration or 0.1 to 0.25 mg of a 1:10,000 solution injected slowly for IV administration, and/or diphenhydramine 50 mg IV with methylprednisolone 100 mg IV (or equivalent), as needed. Subject should be monitored until the investigator is comfortable that the symptoms will not recur. Nivolumab or ipilimumab will be permanently discontinued. Investigators should follow their institutional guidelines for the treatment of anaphylaxis. Remain at bedside and monitor subject until recovery from symptoms. In the case of late-occurring hypersensitivity symptoms (eg, appearance of a localized or

generalized pruritus within 1 week after treatment), symptomatic treatment may be given (eg, oral antihistamine, or corticosteroids).

4.5.8 Treatment Beyond Disease Progression

As described in [Section 1.1.5](#), accumulating evidence indicated a minority of subjects treated with immunotherapy may derive clinical benefit despite initial evidence of progressive disease (PD).⁵³

Subjects treated with the study drugs will be permitted to continue treatment beyond initial PD as assessed by the investigator's clinical judgment and local standards of care as long as they meet the following criteria:

- Investigator-assessed clinical benefit and do not have rapid disease progression
- Tolerance of study drug(s)
- Stable performance status
- Treatment beyond progression will not delay an imminent intervention to prevent serious complications of disease progression (eg, central nervous system [CNS] metastases).
- Subject provides written informed consent prior to receiving additional study treatment using an ICF describing any reasonably foreseeable risk or discomforts or other alternative treatment options
- A radiographic assessment/scan should be performed within 6 weeks of original PD to determine whether there has been a decrease in the tumor size, stable disease, or continued PD. The assessment of clinical benefit should be balanced by clinical judgment as to whether the subject is clinically deteriorating and unlikely to receive any benefit from continued treatment.

For the subjects who continue study therapy beyond progression, further progression is defined as an additional 10% increase in tumor burden with a minimum 5 mm absolute increase from time of initial PD. This includes an increase in the sum of all target lesions and/or the development of new measurable lesions. Treatment should be discontinued permanently upon documentation of further disease progression.

New lesions are considered measurable at the time of initial progression if the longest diameter is at least 10 mm (except for pathological lymph nodes which must have a short axis of at least 15 mm). Any new lesion considered non-measurable at the time of initial progression may become measurable and therefore included in the tumor burden volume if the longest diameter increases to at least 10 mm (except for pathological lymph nodes which must have a short axis of at least 15 mm). In situations where the relative increase in total tumor burden by 10% is solely due to inclusion of new lesions which become measurable, these new lesions must demonstrate an absolute increase of at least 5 mm.

Global deterioration of health status requiring discontinuation of treatment without objective evidence of disease progression at the time should be reported as symptomatic deterioration.

Every effort should be made to document objective progression (ie, radiographic confirmation) even after discontinuation of treatment.

The assessment of clinical benefit should take into account whether the subject is clinically deteriorating and unlikely to receive further benefit from continued treatment. All decisions to continue treatment beyond initial progression must be discussed in the study records, and subjects must sign a separate informed consent form to receive treatment beyond progression.

